### **5.2.2. Disposition Information**

The following tabulations will be provided:

- The number of subjects screened, randomized and not-randomized, with the reason for not being randomized. For all subjects screened only.
- Number (percent) of all randomized subjects per country and investigator by treatment and overall.
- The number of subjects in screened analysis set and number (percent) of subjects in each analysis set (randomized, FAS, PP, [REDACTED] and safety sets), on the “All randomized Analysis Set” as defined in section [3.1](#) by treatment and overall.
- The number (percent) of subjects per analysis window for mRSS as defined in section [3.3.4](#) by treatment and overall.
- The number (percent) of subjects who completed/discontinued the study treatment and the reasons for discontinuation by treatment and overall.
- The number (percent) of subjects who completed the study, subjects who completed the treatment period and entered the OLE study, subjects who completed the treatment period and entered Follow-up phase (i.e. did not entered the OLE study), subjects who completed Follow-up phase and subjects who discontinued the study and the reasons for discontinuation.

### **5.2.3. Protocol Deviations and Eligibility**

Major protocol deviations are determined and recorded while the study is ongoing, and the list is finalized prior to unblinding for the Primary Analysis (although any possible protocol deviations collected between data cut for Primary Analysis and database lock for Final Analysis will continue to be reviewed). For more details, please refer to the Protocol Deviations Plan.

The number (percent) of subjects with major protocol deviations will be tabulated, overall and per class of deviation, by treatment group and overall.

All available information concerning major protocol deviations, deviations on eligibility criteria and subjects not treated will be listed. Protocol deviations leading to exclusion from any analysis set (see section [3.1.5](#)) will be flagged.

---

#### **5.2.4. Inclusion and Exclusion Criteria**

All inclusion and exclusion criteria that subjects did not fulfil will be listed in detail on the All Screened Analysis Set.

#### **5.2.5. Medical History and Concomitant Diseases**

Medical history will be coded using the latest version of the medical dictionary for regulatory activities (MedDRA) as per the data validation manual (DVM). The number and percentage of subjects with any medical history will be summarized overall and for each predefined system organ class (SOC) and preferred term (PT). Frequency tabulations per SOC and PT will be provided for the medical history findings: (i.e., any event with a stop date prior to first IMP intake) as well as for the concomitant diseases (i.e., ongoing conditions or conditions with a stop date on or after first IMP intake).

#### **5.2.6. Prior and Concomitant Medications**

A prior medication is defined as any medication that is taken prior to the first dose of IMP. A concomitant medication is defined as any medication that has a stop date that is on or after the date of first dose of IMP or is ongoing. Medications that started prior to the first dose of IMP and have stop date on or after the first dose of IMP or is ongoing are defined as both prior and concomitant medications.

##### **5.2.6.1. Coding of Reported Terms**

All medications used within 12 weeks prior to and during the screening period will be collected on the electronic case report form (eCRF). All medications will be coded according to the latest World Health Organization Drug Dictionary (WHO-DD).

##### **5.2.6.2. Classification of Medications**

All prior and concomitant medication records will be categorized as follows, considering their date and flags indicating the relative timing versus study (IMP) start or end (before, after, ongoing...):

- Prior only: when the record ended before first IMP administration date.
- Concomitant only: when the record started on or after the first IMP administration date.
- Prior and concomitant: when the record started before the date of first IMP administration, and ended on or after this point, or continued, or if end date is missing.

When the start or end date of the prior and concomitant medication records are incomplete (and no flags indicating relative timing are available), the date of first IMP administration will be considered to the same level of information provided by these incomplete dates to categorize the timing of these records. This means that a record only having month and year will be categorized comparing only to the month and year of the date of first IMP administration. Worst case scenario will be used to categorize concomitant medications: if the same level of information provided by incomplete concomitant medication start date is identical first IMP administration, then the medication will be considered as both prior and concomitant, given end

---

date is not prior to first IMP administration. If the same level of information provided by incomplete concomitant medication end date is identical first IMP administration, then the medication will be considered as both prior and concomitant, given start date is not after to first IMP administration.

#### **5.2.6.3. Calculation of Relative Days**

For both the start and the end dates of the concomitant medication records, their day relative to the day of first IMP administration will be calculated as described in section [3.3.1](#).

#### **5.2.6.4. Presentation of Results**

A frequency tabulation of the anatomical therapeutic chemical (ATC) classes Level 4 by therapeutic subgroup (ATC Level 2) and anatomical main group (ATC Level 1) of the prior medications (defined as ‘prior only’ and ‘prior and concomitant’) will be provided as well as of the concomitant medications (defined as ‘concomitant only’ and ‘prior and concomitant’).

All medications will be listed in detail.

### **5.2.7. Prior and Concomitant Non-Drug Therapies**

#### **5.2.7.1. Coding of Reported Terms**

All non-drug therapies used within 12 weeks prior to and during the screening period will be collected on the electronic case report form (eCRF). All non-drug therapies will be coded according to the latest MedDRA Dictionary.

A prior non-drug therapy is defined as any non-drug therapy that is taken prior to the first dose of IMP. A concomitant non-drug therapy is defined as any non-drug therapy that has a stop date that is on or after the date of first dose of IMP or is ongoing.

#### **5.2.7.2. Classification of Non-Drug Therapies**

All prior and concomitant non-drug therapy records will be categorized as specified in section [5.2.6.2](#).

#### **5.2.7.3. Calculation of Relative Days**

For both the start and the end dates of the concomitant non-drug therapy records, their day relative to the day of first IMP administration will be calculated as described in section [3.3.1](#).

#### **5.2.7.4. Presentation of Results**

A frequency tabulation of the SOC and PT term of non-drug therapies of the prior therapies (defined as ‘prior only’ and ‘prior and concomitant’) will be provided. Similarly, a separate table will be provided for concomitant therapies (defined as ‘concomitant only’ and ‘prior and concomitant’).

All non-drug therapies will be listed in detail.

## 5.2.8. Exposure to IMP and Compliance

### 5.2.8.1. Derivation Rules

#### Derived Parameters: Extent of Exposure to IMP

- *Total treatment duration (days)* = last IMP administration date – first IMP administration date + 1 day.
- *Total treatment duration, excluding days off study IMP*: Number of days with any IMP administration.
- *Total treatment duration, fully compliant (days)*: Number of days with IMP administration, as planned per CSP.

#### Derived Parameters: Compliance

- *Overall compliance (%)* =  $100 \times \left( \frac{\text{number of tablets actually used}}{\text{number of tablets that should have been used}} \right)$

Number of tablets that should have been used will be calculated as:

Total treatment duration \* 3

- *Percentage days with any intake (%)* =  $100 \times \left( \frac{\text{total treatment duration, excluding days off IMP}}{\text{total treatment duration}} \right)$
- *Percentage days fully compliant (%)* =  $100 \times \left( \frac{\text{total treatment duration, fully compliant}}{\text{total treatment duration}} \right)$

Number of tablets actually used will be based on the exposure records collected in the database.

### 5.2.8.2. Presentation of Results

Summary statistics will be provided for each compliance and extent of exposure parameter on the Safety Set.

Frequency tables will be provided for the compliance parameters, using the following categories: <80%;  $80\% \leq x < 100\%$ ; 100%;  $100\% < x \leq 120\%$ ; >120%. Percentages will be calculated out of the number of subjects who were dosed.

## 5.3. EFFICACY ANALYSES

Efficacy analyses will be performed on the FAS. To investigate the impact of non-compliance and protocol violators, a Per-Protocol analysis will also be performed for the primary endpoint, if more than 10% of the subjects have at least one major protocol deviation leading to exclusion to the PP Analysis Set.

Tabulations will be shown per treatment group.

---

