### Visit 9 (Week 24)

- If Visit 9 (Week 24) cannot be conducted within the time window of  $\pm 4$  days, the visit window can be extended to  $\pm 28$  days (i.e. can be extended or shortened up to 28 days) to enable conduct of the visit on site.
- If Visit 9 is performed after Week 24, additional IMP may be required. This may be shipped by the site directly to the subject as detailed in Section 5.3.
- For the rollover of a subject into the GLPG1690-CL-206 Open-Label Extension study, a complete, on-site rollover visit is required. If Visit 9 cannot be conducted on site within the extended window of Week 24 +28 days, the subject will be given the opportunity to rollover into the Open-Label Extension study until Week 32. The subject will however be off study medication and not receive IMP between Week 28 to 32. The Visit 9/rollover assessments should be performed at this on-site visit.
- If the rollover visit cannot be scheduled before Week 32, the subject cannot rollover and will continue in the follow-up period of GLPG1690-CL-204 with a first follow-up visit 4 weeks after last IMP administration.
- The follow-up visits need to be scheduled in relation to the last dose of IMP. Follow-up visit 1 should be 28 days  $\pm 7$  days after the last IMP administration, and Follow-up visit 2 should be 84 days  $\pm 7$  days after the last IMP administration.

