e Triplicate ECGs will be performed irrespective of IMP intake at Visit 1 (screening), within 30 minutes before IMP intake and between 2 to 3 hours after IMP intake at Visit 2 (baseline) and Visit 3. A single ECG will be performed within 30 minutes before IMP intake at Visits 7 and 9, and irrespective of IMP intake at ED (if applicable) and Follow-up Visit 1.

i If Visit 9 (Week 24) cannot be conducted within the time window of ±4 days, the visit window can be extended to ±28 days (i.e. can be extended or shortened up to 28 days) to enable conduct of the visit on site. If Visit 9 is conducted after Week 24, additional regular phone calls at Week 24 and every 14 days thereafter should be implemented, until an on-site Visit 9 can take place, or until Week 32, to evaluate the subject's safety. In addition, if any of the follow-up visits cannot be performed on-site, a phone call to evaluate the subject's safety should be performed on the date of the visit. The information to be collected during these phone calls is detailed in Section 6.6.

j The FU visits need to be scheduled in relation to the last dose of IMP. FU1 should be 28 days ±7 days after the last IMP administration, and FU2 should be 84 days ±7 days after the last IMP administration.

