#### **7.2.5. Per-Protocol Set**

All Full Analysis Set subjects who did not have a major protocol deviation that impacts the efficacy results (as defined in a protocol deviation plan). The determination of the per-protocol population will be finalized and documented prior to database lock and unblinding.

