## 5. STATISTICAL ANALYSES

### 5.1. CHANGES TO THE PLANNED ANALYSES, NOT COVERED BY PROTOCOL AMENDMENTS

- All Enrolled Analysis Set will not be used for the analyses so not included in SAP.
- All Randomized Analysis Set will be used for the presentation and summary of the baseline assessments to better interpret the study data.
- Definition of Per-Protocol Analysis Set was slightly modified within this SAP text as unblinding will occur at the time of primary analysis, i.e. not at the same time of database lock.
- Definition of Per-Protocol Analysis Set was modified to exclude subjects who had mRSS assessment at Week 24 outside of the original time window of [142, 183] study day.

- An additional sensitivity analysis for the primary endpoint was added where for subjects that did not have a Week 24 mRSS assessment at all within the extended window, but possibly in the Week 28 - Week 32 interval, their Week 28 result will be allocated to Week 24 analysis visit.

---

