#### 5.3.2.3. Analysis Methods

The following analyses will be done on the FAS as the primary analysis, and repeated on the PP Analysis Set, if more than 10% of the subjects have at least one major protocol deviation, to confirm the results of the primary analysis:

The mRSS and change from baseline in mRSS score (primary endpoint) will be summarized by descriptive statistics. Mean ( $\pm$ SE) plots over time (analysis visits based on time window) for both treatment groups, and similar mean ( $\pm$ SE) plots for the change from baseline will be presented. Additionally, spaghetti plot of change from baseline will be displayed with subjects presented by treatment.

Change from baseline in mRSS will be analyzed using a mixed-effects model for repeated measures (MMRM). The model will include treatment and visit as fixed effects, baseline mRSS and country as covariates, and treatment-visit as interaction terms. Subject will be included in the model as a random effect. The likelihood-based MMRM will be performed using a SAS PROC MIXED procedure (see [Appendix 3](#)), and the Kenward-Roger method for degrees of freedom will be applied. The restricted maximum likelihood (REML) method will be used for estimation. The Least Square (LS) means along with the associated SE and 95% CIs, as well as the difference in LS means and associated 95% CIs will be displayed at each time point. For exploratory purpose only, p-values will also be displayed for testing the difference in LS means at each timepoint. The p-value derived for the overall difference between treatment groups will also be displayed, as well as all p-values for fixed effects included in the model.

The variance-covariance matrix will be assumed to be unstructured. If the procedure does not converge then a compound symmetric variance-covariance matrix will be used instead.

The number and percentage of subjects with a clinically meaningful change in skin score (as defined in section 5.3.2.2) will be summarized by treatment. Incidence will be derived overall (at any post-baseline timepoint) and for each analysis visit.

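### The trigger for the per-protocol repeat counts only major deviations, so permitted late Week 24 visits that SAP 5.1 removes from the PP set do not appear to count towards it

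*SAP*

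**What the plan says.** The PP analysis is conditional, and the condition is written twice. SAP 5.3 (Efficacy Analyses) runs it for the primary mRSS analysis "if more than 10% of the subjects have at least one major protocol deviation leading to exclusion to the PP Analysis Set". SAP 5.3.2.3 (Analysis Methods) says the FAS analyses are "repeated on the PP Analysis Set, if more than 10% of the subjects have at least one major protocol deviation". The second wording does not require that the deviation leads to exclusion. Both are expressed only in major protocol deviations.

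Membership of the PP set is wider than that. Protocol 7.2.5 removes FAS subjects with a major deviation affecting efficacy, as set out in a separate deviation plan. SAP 5.1 then changes the definition so that it also removes subjects whose Week 24 mRSS lies "outside of the original time window of [142, 183] study day".

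Protocol 6.1 and footnote i of the Schedule of Activities allow Visit 9, for a COVID-19-related reason, to move beyond the usual ±4 days: the window "can be extended or shortened up to 28 days". SAP Table 2 assigns mRSS scores on Days 142 to 197 to the Week 24 analysis visit.

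**The concern.** The list of reasons for leaving the PP set and the count that decides whether the PP analysis is run do not match. SAP 5.1 lengthened the list; the two trigger sentences were not changed with it. A subject with a permitted late Visit 9 is on the list but, as the text reads, not in the count.

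What is at stake is a supportive check. Scores from Days 184 to 197 enter the FAS analysis as Week 24 values. In the available text, the PP repeat is the only analysis that takes them out. If late visits are common and major deviations are few, the plan as written omits that check in the very case where the added exclusion has most to do.

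**Working it through.** **Design figure.** The plan gives no figure for the trigger. Its one derived design figure, a 63% probability of observing more than 4 points, is reproduced with 20 and 10 subjects less 10% dropout (18 and 9), SD 5 and a true difference of 4.7: Φ((4.7 − 4) / (5 × √(1/18 + 1/9))) = Φ(0.7 / 2.041) = 63.4%. This confirms the planned size of 30 used below. It is not in dispute.

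**Windows, in study days (target Day 169).**
- Usual Visit 9 window (Protocol 6.1): 169 ± 4 = Days 165 to 173.
- Extended window for a COVID-19-related reason: 169 ± 28 = Days 141 to 197.
- Week 24 analysis window for mRSS (SAP Table 2): Days 142 to 197.
- Window required for the PP set (SAP 5.1): Days 142 to 183.

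The gap is therefore Days 184 to 197. A Visit 9 held then under the allowance is permitted by the protocol, is analysed as Week 24 in the FAS, and is outside the PP set.

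**Does another analysis drop these scores?** SAP 5.3.3.1.1 adds a sensitivity analysis for subjects with no Week 24 assessment in the extended window, bringing in scores up to Day 225. It adds later scores and removes none. The derived-mRSS analysis in the same section deals with missing items. Neither covers Days 184 to 197.

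**Trigger arithmetic.** The denominator is not stated; the FAS, taken as 30, is assumed. Since 3/30 = 10.0% is not more than 10%, at least 4 subjects are needed (4/30 = 13.3%). The numbers of late visits and deviators below are illustrative, and each row assumes no further major deviations.

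| Excluding major deviators | Permitted visits on Days 184–197 | Outside PP set | Trigger count | PP repeat run? |
|---|---|---|---|---|
| 0 | 6 | 6/30 = 20% | 0/30 = 0% | No |
| 3 | 1 | 4/30 = 13.3% | 3/30 = 10.0% | No |
| 3 | 6 | 9/30 = 30% | 3/30 = 10.0% | No |

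If every PP exclusion were counted, all three rows would exceed 10%. The SAP 5.3.2.3 wording fires more easily: in the second and third rows, one further major deviation that does not lead to exclusion would give 4/30. It still does not count the late visits themselves, and the first row stays at zero under either wording.

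**The case against.** The strongest objection is that the governing text is not available. The SAP contents list 3.1.4 (Per-Protocol Analysis Set), but its text is not in the copy reviewed. SAP 5.1 is only a summary of the change, and major deviations are defined in a Protocol Deviations Plan held separately. If either document applies the Day 142 to 183 rule by classing those subjects as major deviators, they do count. This stands, and the conclusion is conditional on it. Such a classification would, however, sit badly with a protocol that permits the visit. A visit on Days 184 to 197 without a COVID-19-related reason is a different matter: it is outside ±4 days and could properly be recorded as a deviation.

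It is also fair to say that SAP 5.3 gives the purpose of the PP analysis as non-compliance and protocol violators, not late scores, and that SAP 5.1 gives no reason for the window exclusion. A link with COVID-19 delays is an inference. Protocol 5.3 provides for IMP supply to cover a delayed visit, so a late score may still be an on-treatment score.

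A reader might go further and infer that the pooled 10% threshold is itself an error, because 3 of 10 placebo subjects (30%) could be excluded while the count reads 3/30 = 10.0%. The arithmetic is right, but the documents do not support calling it an error. A pooled threshold is a design preference that no passage contradicts. It can be judged from the deviation list, which SAP 5.2.3 finalises before unblinding, whereas a per-arm threshold needs the treatment codes. SAP 5.2.2 and 5.2.3 already tabulate analysis-set membership and major deviations by arm, so an imbalance would be seen. It is also a worst case: if three deviators fell at random among 30 subjects, all three would be on placebo with probability 3.0%. Attaching a shift in the placebo mean to that case would need an assumed difference between excluded and retained subjects that no document provides.

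**Conclusion.** The point holds in a limited form. On the available text, subjects with a permitted Visit 9 on Days 184 to 197 leave the PP set without counting towards the trigger, so following the plan can omit the only analysis seen to drop their Week 24 scores. Six such visits with no deviators would put 20% of 30 subjects outside the PP set at a trigger count of zero.

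This rests on three assumptions: that neither SAP 3.1.4 nor the Protocol Deviations Plan classes these visits as major deviations; that the denominator is an FAS of about 30; and that late visits occur in some number, which the documents do not predict.

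A reader might infer that the primary result is at risk. It is not. The FAS analysis is primary and is the same whether or not the PP repeat is run, and SAP 5.3.1 describes an exploratory study judged on all its results. Severity is minor: a supportive analysis only.

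**What to change.** Replace the trigger in both SAP 5.3 and SAP 5.3.2.3 with one rule, which also removes the difference between the two wordings:

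*The primary analysis is repeated on the PP Analysis Set whenever any FAS subject is excluded from it, for any reason (major deviation or Week 24 mRSS outside Days 142–183).*

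If a pooled 10% threshold is preferred, count all PP exclusions towards it and state the denominator. A per-arm threshold is not recommended, because it could be evaluated only after unblinding. The change should be made before unblinding for the primary analysis. If SAP 3.1.4 or the Protocol Deviations Plan already counts these visits as major deviations, a sentence saying so in SAP 5.3 would deal with the late-visit gap, though the two trigger wordings would still need to agree.

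The cost is a wording change in two places and at most one extra run of a model already specified. The drawback is that, when few subjects are excluded, the PP result may differ little from the FAS result and add little to the report.

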### 5.3.1. Level of Significance

All statistical tests will be 2-sided and performed at the 5% significance level, thereby providing 95% (2-sided) CIs. However, given the exploratory nature of this proof-of-concept study, the success of the study will be based on the evaluation of all analysis results, including safety profile and descriptive analysis of all efficacy endpoints.

### 5.3.2. Primary Efficacy Parameter

#### 5.3.2.1. Definition

The primary endpoint of the study is the change from baseline in mRSS over 24 weeks. This is collected at the time points specified in the Schedule of Activities (see [Appendix 1](#)).

For individual subjects, clinically meaningful changes in skin score (MCID) are 4.7 skin score units and/or at least 20% change in overall mRSS. Only decreases from baseline will be deemed clinically meaningful changes in skin score.

